#### 3.4.3 Derived variables

Variable	Original data	Description of derived data	Algorithm to develop/Detail for implementation
Body mass index (BMI [kg/m^2])	Measured height and weight. (Demographics data at baseline)	Weight (kg) / (Height [cm]/100) 	NA

Physical activity, including stair climbing	Continuous accelerometer measurement, self-reported activities	Classification algorithm, similar to the one described in (5)	An activity flag is extracted from the accelerometer by Vivalink, by using a predefined threshold for adult movement. For stair climbing, first periodic movement must be determined, by using frequency analysis on specific time windows, and generating a ratio to the total spectrum indicating periodic activity over a certain threshold (See (5) for more details). Climbing of stairs is determined by a classification algorithm, here a tree classifier and a nearest neighbors classifier will be tested, using the activity labels inputted by the patient for supervised learning.
Heart rate	ECG	Beats per minute.	Heart rate is provided by Vivalink. In case it needs to be calculated (e.g., for initial comparison of results obtained), the process to follow is to use the heartpy python package, by using the 'process' method. See (6) for details on how to use the package. Said method returns two datasets, one of them being the measures, where one can extract the beats per minute (bpm).  <code>working_data, measures = heartpy.process(ecg_data, ecg_fs)</code> <code>Heart_Rate= measures['bpm']</code> Where ecg_fs is the sample rate of the ECG, 128 in this case.
Resting heart rate	Accelerometer, ECG	Resting state as determined by accelerometer, Beats per minute extracted from ECG	The resting heart rate is calculated as described in the heart rate calculation, but is calculated only in periods where the activity flag is 0.
Heart rate variability reflecting differences in time intervals between 2 R-waves in the ECG (milliseconds)  SDRR, SDNN, SDNNI, RMSSD, ln(RMSSD), pNN50, SI, LF power, HF power, LF/HF	ECG	For details of calculation see (7)	ECG peaks are calculated as explained for the heart rate calculation. The inter beat time (inter peak) is measured - RR- and the measures derived from it are:  SDRR, the standard deviation of intervals between heartbeats  SDNN, the standard deviation of intervals between heartbeats, after removing abnormal beats  $SDNN = \sqrt{\frac{1}{X-1} \sum_{i=1}^X (NN_i - \bar{NN})^2}$  SDNNI, mean of the standard deviations of all the NN intervals for each 5 min segment of a 24-h HRV recording  RMSSD, the root mean square of successive differences between adjacent N-N intervals  $RMSSD = \sqrt{\frac{1}{X-1} \sum_{i=1}^X (NNdiff_i)^2}$  ln(RMSSD), natural logarithm of RMSDD

			
pNN50, percentage of adjacent NN intervals that differ from each other by more than 50 ms
 
SI, the Baevsky's stress index, calculated as <math>AMo / 2Mo \times MxDMn</math>. Where <math>AMo</math> is the amplitude of the mode presented in percent in comparison to all other RR intervals. <math>Mo</math> is the mode of the RR intervals. <math>MxDMn</math> is the difference between the maximum and minimum measured RR interval.
 

 
(8)
 
Applying a Fast Fourier Transformation (FFT) or autoregressive (AR) modeling one can separate HRV into its component ULF, VLF, LF, and HF rhythms that operate within different frequency ranges. Given in absolute values of power (milliseconds squared).
 
LF power, low frequency power (0.04–0.15 Hz)  HF power, high frequency power (0.15–0.40 Hz)
 
LF/HF Ratio, spectral HRV index computed as (LF/HF)

Tempera-ture	Display temperature	Relative values	Temperature is provided by Vivalink. The value for temperature is derived by Vivalink from the display temperature and then calibrated using initial calibration values, in an IP protected process. The sensor temperature is considered only as a relative value to evaluate changes in the temperature, and not as an objective human body temperature value, meaning no thresholds relative to normal human body temperature are considered, and it will not be used as a marker for fever or hypothermia.
Respiration rate	ECG	Measure of R-R peaks, and application of algorithms as the ones described in (9)	Respiration rate is provided by Vivalink. In case it needs to be calculated, the process to follow is to use the heartpy python package, by using the 'process' method. See (6) for details on how to use the package. Said method returns two datasets, one of them being the measures, where one can extract the breathing rate. <code>working_data, measures = heartpy.process(ecg_data, ecg_fs)</code>

---

			
Resp_rate = measures['breathingrate'] Where ecg_fs is the sample rate of the ecg, 128 in this case.

Ratio of in- vs expiration time	ECG	Measure of R-R peaks, and application of algorithms as the ones described in (9)	
This measure will be calculated with the heartpy python package, by using the 'process' method. See (6) for details on how to use the package. Said method returns two datasets, one of them being the measures, where one can extract the breathing signal.
 <pre>working_data, measures = heartpy.process(ecg_data, ecg_fs)</pre> 
breathing_signal = working_data['breathing_signal'] Where ecg_fs is the sample rate of the ecg, 128 in this case.
 
Using the breathing signal one can determine the inspiration and expiration peaks (using the peak finder python package scipy.signal.find_peaks, see (10)). The difference between said peaks in milliseconds can be used to determine the ratio of inspiration (distance from lower point to next peak) vs expiration (distance from peak to next lower point). The average, mode, max and min of said ratios will be reported.

Cough frequency	Accelerometer, ECG, self-reported activities	Predictive algorithm similar to the one described in (11)	
Accelerometer and ECG signals are filtered to reduce noise from the sensor wear, different filters must be tested to see which one works best for this specific data, including low pass, high pass, bandpass and notch filters. Features are extracted by both dimensionality reduction (PCA, NMF) and frequency analysis, specifically, windows of 2 or 5 seconds can be taken where measures as mean, median, sd, skewness, kurtosis, etc. are calculated for the first and second component, and the predominant frequency of a window is considered, as well as the magnitude of the signals, and used as features to train a supervised classifier (using the activity labels inputted by the patients). This technique will be tested with random forest, gradient boosting and other boosting methods.

Sleep pattern	Accelerometer, self-reported activities	Self-reported going to bed and waking up, combined with accelerometer data to improve accuracy of sleeping time, plus accelerometer analysis to infer sleep quality.	The basis of the sleep pattern calculations is the self-reported bedtimes. With the same technique as the cough frequency prediction, inactivity signals can be predicted from the labeled data to improve the bedtime accuracy, and the changes in accelerometer (step detection algorithms) can be used to quantify the number of clear breaks in the sleep (standing up, strong cough, etc.). In addition, HR and HRV will be analyzed for unusual patterns (e.g., sudden stronger increases in HR could either be indicative for waking up, or from experiencing sleep apnea. HR can also be used to support information from the accelerometer regarding getting up for example. Expected HR changes during REM phases may be considered. HRV would be expected to increase during sleep. Likewise, temperature changes may support the above analyses. ML algorithms (semi-supervised / self-learning) for classifying periods of sleep disturbances may be explored after building an initial label set using observer consent on periods of sleep disturbance. The result will be the number of hours sleeping per day, a qualifier between 1 and 3 of sleep quality using the average movement during self-reported sleeping hours, being 1 below average movement, 2 average movement, and 3 above average movement and the number and duration of phases of sleep disturbance.
Frequency of additional medication	Self-reported activities	Self-reported use of additional medication	Count of the number of times the use of additional medication (Bedarfsmedikament) as a log activity is reported per day.

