Intended purpose	
Below in italics is the intended purpose of the CE marked Model VV-330 as supplied by VivaLNK. The device to be used in the study, includes a temperature monitoring algorithm not covered by the CE marked device described below.
 
"Medical Wearable Platform SDK-01 is intended to record, store and transfer electrocardiogram (ECG) and accelerometer data. The platform has the capability to provide Heart Rate, Respiratory Rate and R-R Interval using the ECG rhythm. The ECG recorder patch is an ambulatory, continuous recording patch, intended for at-home or hospital, by clinicians or health professionals who intend to monitor their patient's physiological and health conditions for an extended period of time. The device is not intended for patients under 18 years old. This Instructions for Use is only limited to the use of the hardware and the Software Development Kit (SDK). It does not include any information about the mobile application or user interfacing device as that is outside the scope of the system."

The period of validity of CE certificate for model VV-330.	Issue date: 2019-11-08 Expiry Date: 2024-05-26

NOTE: the model to be used in the study has been modified from the CE marked device to add an temperature monitoring algorithm (a software only change).	
Statement of deviation from the CE marked device	The device used in the study will be the same as the CE marked model VV-330 with the addition of temperature monitoring capabilities. A temperature sensor already present in the model VV-330 has been "activated" by the addition of an algorithm. The temperature sensor was already physically present in the wearable patch at the time of the CE mark, but was not turned on, tested or evaluated by the Notified Body for the current CE mark status.
Description of device materials in contact with body tissues	Body-contacting materials are on the Adhesive, which includes proprietary textile and medical-grade adhesive layers with hydrogel conductive contacts.
Statement that this device does not include any medicinal substances, human or animal tissues or their derivatives, or other biological active substances	"Our device does not include any medicinal substances, human or animal tissues or their derivatives, or other biological active substances."

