- Respiratory Rate

Using the raw data and participant labelling information, a number of further derived data will be generated by Merck as listed under variables.

Participants in the COPD and calibration cohorts will receive their devices at study inclusion, be instructed on use and return the devices at study end. Data will be collected continuously during the study.

Security of data transmission and storage

Data transmission and storage will comply to EU-General Data Protection Regulation (EU-GDPR) and to the German “Bundesdatenschutzgesetz” BDSG. Data from the medical device will be transmitted in encrypted and pseudonymized way. Servers for data storage will be located in Europe, and data stored in a secure encrypted format.

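### The SAP specifies no refinement of R-peak times on a 128 Hz ECG; if peaks stay on the sample grid, low RMSSD values are inflated and their falls understated

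*SAP*

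**What the plan says.** The heart rate row of the table in SAP 3.4.3 (Derived variables) says that the device maker supplies heart rate. As a fallback it gives the call "working_data, measures = heartpy.process(ecg_data, ecg_fs"), whose only arguments are the signal and the sampling rate. The rate is then stated: "Where ecg_fs is the sample rate of the ECG, 128 in this case".

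The HRV row uses the same peaks: "ECG peaks are calculated as explained for the heart rate calculation". It continues "The inter beat time (inter peak) is measured" and lists ten measures derived from these intervals. One is defined as "RMSSD, the root mean square of successive differences between adjacent N-N intervals"; ln(RMSSD), HF power and LF/HF are also on the list. The row cites outside sources for calculation details. It specifies no up-sampling, interpolation or peak-time resolution.

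For HRV this is the stated route, not a fallback. Protocol 9.6.2 names heart rate, physical activity and respiratory rate as the derived data from the device maker, and adds: "Using the raw data and participant labelling information, a number of further derived data will be generated by Merck as listed under variables". Protocol 9.2.2 (Table 3) reports for the CE-marked model: "The platform has the capability to provide Heart Rate, Respiratory Rate and R-R Interval using the ECG rhythm". The resolution of those R-R intervals is not given, and the SAP does not use them for HRV.

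**The concern.** At 128 samples per second, adjacent samples are almost 8 ms apart. That does not matter for mean heart rate. RMSSD, however, is built from small differences between successive intervals, and a peak time rounded to the nearest sample puts an error into each of them.

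The rounding always adds variance, so it pushes RMSSD upward. Averaging over a day does not remove it. The bias is proportionally largest where variability is lowest, so it flattens low values and makes a fall look smaller than it is. HRV is named in Objectives 1, 3 and 4 and is among the model inputs for Objectives 2 and 5. SAP 3.4.5.1 gives it ten variables in the primary descriptive tables, which look for change within 14 days before onset.

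**Working it through.** The documents state no precision or expected level for HRV, so there is no planned figure to reproduce first.

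**Inputs**
- Sampling rate 128 Hz (SAP 3.4.3), so one sample is T = 1000/128 = 7.8125 ms.
- RMSSD is the root mean square of successive R-R differences (SAP 3.4.3).
- Assumption A: each peak time is the nearest sample, with no refinement.
- Assumption B: true RMSSD lies between 5 and 30 ms.

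**Timing error**
1. Error of one peak, uniform over a sample: SD = T/√12 = 7.8125/3.464 = 2.26 ms.
2. A successive R-R difference combines three peak times with weights 1, −2, 1. The squared weights sum to 6, so its error SD = 2.26 × √6 = T/√2 = 5.52 ms.
3. The error adds in quadrature: read RMSSD = √(true² + 5.52²) = √(true² + 30.5).

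A simulation of 200,000 beats rounded to the 128 Hz grid agrees. With almost no true beat-to-beat variation it reads 5.43 ms, and a true 10.02 ms reads 11.43 ms.

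**Levels**

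| True RMSSD (ms) | Read (ms) | Inflation |
|---|---|---|
| 5 | 7.45 | +49.0% |
| 10 | 11.42 | +14.2% |
| 15 | 15.98 | +6.6% |
| 20 | 20.75 | +3.7% |
| 30 | 30.50 | +1.7% |

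**Falls**

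| True fall (ms) | True % | Read (ms) | Read % | ln fall, true | ln fall, read |
|---|---|---|---|---|---|
| 10 to 7 | −30% | 11.42 to 8.92 | −22% | 0.357 | 0.248 |
| 20 to 15 | −25% | 20.75 to 15.98 | −23% | 0.288 | 0.261 |
| 30 to 20 | −33% | 30.50 to 20.75 | −32% | 0.405 | 0.385 |

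**Other HRV measures**
- SDNN: at about 30 ms it moved by less than 0.2 ms in simulation.
- pNN50: it moved by at most 0.15 percentage points.
- HF and LF power: the rounding error in R-R has one-sided spectral density (2T²/12)/f_b × (2 − 2cos(2πf/f_b)), where f_b is beats per second. Integrated over 0.15–0.40 Hz, this adds about 5.8, 3.4 and 2.1 ms² to HF power at 60, 75 and 90 beats per minute. Over 0.04–0.15 Hz it adds 0.4, 0.2 and 0.1 ms² to LF power. LF/HF is therefore pushed down when true HF power is low. The documents give no expected HF power, so no percentage is offered.

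**With refinement**
- On a 1 ms grid the floor is 1/√2 = 0.71 ms, and a true RMSSD of 5 ms reads √(25 + 0.5) = 5.05 ms (+1%).
- For synthetic R waves sampled at 128 Hz with 1% noise, a parabola through three samples returned a true RMSSD of about 5 ms as 5.00 to 5.07 ms. The grid alone gave 7.41 to 7.60 ms.

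**The case against.** **Absence of interpolation is inferred from silence.** This stands. A reader might take the plan to say that HRV is computed without interpolation. It does not: it shows a call with no refinement option and points to outside documentation. The package could not be run here, so its default behaviour was not checked. If it refines peak times, the floor largely disappears. The finding is therefore conditional.

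**Not all of HRV is affected.** This also stands. The effect is confined to RMSSD, ln(RMSSD), HF power and LF/HF.

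**The size depends on values that the documents do not give.** True. Eligibility runs from 40 to 80 years, and nothing in the plan shows that participants will have RMSSD near 5 or 10 ms. From 20 ms upward, inflation is below 4%.

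**The prediction model and the correlations are hardly affected.** A reader might infer that Primary Objective 2 is compromised. With a fixed floor, the read value rises steadily with the true one, so ranks are kept; tree-based splits and Kendall's tau scarcely change. For Pearson's coefficient, assume lognormal true RMSSD with median 8 to 30 ms and log-SD 0.3 to 0.5. True and read values then correlate at 0.997 or more, and at 0.979 or more on the log scale. Substantial loss in Objectives 2 or 3 is not supported.

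**It can be repaired later, and the study is exploratory.** Raw ECG is a primary device output (Protocol 9.6.2), so peaks can be refined at any time. That lowers the severity. It does not argue against writing the better method into the plan, because reported RMSSD levels and changes would otherwise depend on an unstated software detail.

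**Conclusion.** The concern holds as a conditional and minor one. SAP 3.4.3 fixes the sampling rate and the peak-detection call but specifies no peak-time refinement. If peaks stay on the grid, an error of 5.52 ms adds in quadrature to RMSSD; RMSSD does not rise by 5.5 ms. The bias matters below roughly 10 to 15 ms and is small from 20 ms upward.

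The consequences lie mainly in the RMSSD levels and the pre- and post-exacerbation changes described under Objective 1, and in the scale of the mixed-model coefficients under Objective 4. The conclusion rests on two assumptions: peaks are not refined by default, and some participants have low RMSSD. The documents settle neither.

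**What to change.** Add one sentence to the HRV row of SAP 3.4.3: before R-R intervals are formed for the HRV measures, each R-peak time is refined to about 1 ms by interpolating the ECG around the peak, for example with a parabola or a cubic spline. If the R-R intervals are instead taken from the device platform, state that source and its time resolution.

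The cost is one SAP sentence and a little extra computing. No new data are needed, because the raw ECG is already collected.

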9.3 Variables

The following variables will be collected for this study (pending availability):

Several biometric parameters will be measured in a time-dependent manner using the Vivalink wearable device. Values measured from day 8 to 14 will be used as baseline data (e.g. for determining parameter changes during the observation period or as co-factor in model building) unless this time period is within a 2-week distance of an exacerbation. In this case the next 7-day period with a distance of 4 weeks from an exacerbation will be considered the baseline in this context.

Variables measured with the Vivalink wearable device (including, but not limited to):

- Physical activity including stair climbing, (calculated based on continuous accelerometer measurement) [daily average] (derived parameter)
- Heart rate as beats per minute [daily average] (derived parameter)
- Resting heart rate (resting state as determined by accelerometer, beats per minute) [daily average] (derived parameter)
- Heart rate variability reflecting differences in time intervals between 2 R-waves in the ECG (milliseconds) [daily average (where applicable) of the following parameters: SDRR (standard deviation of RR intervals), SDNN (standard deviation of NN intervals), SDNNI (Mean of the standard deviations of all the NN intervals for each 5 min segment of a 24 h HRV recording), RMSSD (Root Mean Sum of Squared Distance), ln(RMSSD) (natural logarithm of RMSSD), pNN50 (percentage of successive RR intervals that differ by more than 50 ms) SI (stress index), LF power (low frequency fraction of HRV, 0.04 – 0.15 Hz), HF power (high frequency portion of HRV, 0.15 – 0.40 Hz), LF/HF (ratio of LF-to-HF power); for details of calculation check see [Shaffer 2017](#)] (derived parameters).
- Temperature [daily average, minimum -maximum values]
- Respiration rate (breath per minute) [daily average, minimum -maximum values] (derived parameter)
- Ratio of inspiration vs expiration time [daily average min-max] (derived parameter)
- Cough frequency (derived parameter)
- Sleep pattern (derived parameter)

Self-measured Variables:

- Self-reported COPD symptoms via the CAT questionnaire
- Self-reported activities (coughing, coughing with sputum production, spray use, non scheduled spray use, eating, going to bed, waking up, walking, climbing stairs, and physical exercise) as collected by the participant app
- Self-reported satisfaction with the study, collected via end of study questionnaire

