#### 2.1.4 Sensor measurements by Vivalink wearable device and ePRO diary

Unless indicated otherwise, the following variables are measured continuously throughout the observation period.

- Physical activity including stair climbing, (calculated based on continuous accelerometer measurement) [daily average] (derived parameter)

- Heart rate as beats per minute [daily average]
- Resting heart rate (resting state as determined by accelerometer, beats per minute) [daily average] (derived parameter)
- Heart rate variability reflecting differences in time intervals between 2 R-waves in the ECG (milliseconds) [daily average] of the following parameters:
  - SDRR (standard deviation of RR intervals),
  - SDNN (standard deviation of NN intervals),
  - SDNNI (Mean of the standard deviations of all the NN intervals for each 5 min segment of a 24 h HRV recording),
  - RMSSD (Root Mean Sum of Squared Distance),
  - ln(RMSSD) (natural logarithm of RMSSD),
  - pNN50 (percentage of successive RR intervals that differ by more than 50 ms)
  - SI (stress index),
  - LF power (low frequency fraction of HRV, 0.04 – 0.15 Hz),
  - HF power (high frequency portion of HRV, 0.15 – 0.40 Hz),
  - LF/HF (ratio of LF-to-HF power) (derived parameter)
- Temperature [daily average, minimum and maximum values] (derived parameter)
- Respiration rate (breath per minute) [daily average, minimum and maximum values]
- Ratio of in- vs expiration time [daily average, minimum and maximum values] (derived parameter)
- Cough frequency (derived parameter, count per day)
- Sleep pattern (derived parameter, hours of sleep)
- Self-reported activities as collected by the participant app, logged as activity per time-stamp, allowing for several logs of the same activity per day:
  - coughing,
  - coughing with sputum production,
  - spray use,
  - non-scheduled spray use,
  - eating,
  - going to bed,
  - waking up,
  - walking,
  - climbing stairs,
  - and physical exercise

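### The stress index is printed without brackets, is defined on RR rather than NN intervals and has no stated window or bin width; read literally, it largely cancels the variability it should measure

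*SAP*

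**What the plan says.** The heart rate variability row of SAP 3.4.3 has a column for implementation detail. There it introduces the index with "SI, the Baevsky's stress index, calculated as" and prints AMo / 2Mo × MxDMn on one line. It then defines the terms. AMo is the height of the mode, expressed as a percentage relative to the other RR intervals, and Mo is the modal RR interval. The third term, the range, "is the difference between the maximum and minimum measured RR interval".

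The same cell defines "SDNN, the standard deviation of intervals between heartbeats, after removing abnormal beats", and uses NN intervals for SDNNI, RMSSD and pNN50 as well. It writes no beat-removal step for the stress index.

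On the time unit, SAP 2.1.4 lists the index under "Heart rate variability reflecting differences in time intervals between 2 R-waves in the ECG (milliseconds) [daily average] of the following parameters". Protocol 9.3 has "daily average (where applicable) of the following parameters". Only SDNNI has a segment length (5 minutes). No histogram bin width is given for the mode or its amplitude.

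**The concern.** There are two separate problems.

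**The formula.** By ordinary precedence, the printed string multiplies by the range. AMo is the share of intervals at the mode, so it grows as the RR distribution narrows. The range shrinks as the distribution narrows. Their product therefore hardly responds to variability, whereas a quotient responds strongly.

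**The input.** A range depends on only two intervals. One missed R peak merges two intervals into one of about double length and can become the maximum. The cell separates RR from NN intervals and assigns the index to RR, so nothing in the text protects it from such beats. Protocol 9.9 itself expects misplaced devices and undetected technical errors.

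The index is one of the ten HRV variables tabulated for primary objective 1 (SAP 3.4.5.1) and belongs to the 17 sensor variables correlated in objective 3 (SAP 3.4.5.3). It is also a candidate feature in objective 2, because SAP 3.4.2 admits all available features. A programmer working from the cell as written could produce a table that says little about variability.

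**Working it through.** The SAP gives no numerical value for the index, so there is no figure to reproduce. The check compares two readings on simulated RR series:

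- printed: (AMo / 2Mo) × MxDMn
- denominator: AMo / (2 × Mo × MxDMn)

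**Inputs.** The component definitions come from SAP 3.4.3. The ECG sample rate of 128 per second is also from SAP 3.4.3 and gives a resolution of 1/128 s = 7.8 ms. Assumed: normal RR intervals with mean 800 ms, bins of 7.8 or 50 ms, and windows of 375 beats (5 minutes) or 108,000 beats (24 hours). Mo and MxDMn are in seconds; relative changes do not depend on the unit.

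**Step 1: what to expect.** With fine bins, AMo is proportional to 1/SD, and for a fixed number of beats the range is proportional to SD. The printed form is then proportional to (1/SD) × SD, a constant. The denominator form is proportional to 1/SD². If SD falls by 30%, the denominator form changes by 1/0.7² = 2.04, or +104%, and the printed form by nothing.

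**Step 2: RR SD raised six-fold, from 20 to 120 ms.**

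| Bin, window | Printed | Denominator |
|---|---|---|
| 50 ms, 5 min | 3.8 to 7.7 | 272 to 15.5 |
| 50 ms, 24 h | 5.4 to 11.0 | 173 to 9.7 |
| 7.8 ms, 5 min | 1.23 to 1.85 | 87.8 to 3.7 |
| 7.8 ms, 24 h | 1.71 to 1.74 | 55.3 to 1.6 |

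Cancellation is almost complete with fine bins over 24 hours. In the other rows a 1.5- to 2-fold residual remains, and it runs in the opposite direction to the denominator form.

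**Step 3: a 30% fall in spread** (starting SD 50 or 100 ms, same bins and windows). The printed form changes by about -14% to -1%, the denominator form by about +77% to +103%. The upper end agrees with step 1.

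**Step 4: one missed beat, one 24-hour window, 50-ms bins.** At SD 40 ms the range goes from 0.36 to 0.97 s, which multiplies the printed form by 2.7 and the denominator form by 0.37. At SD 80 ms the range goes from 0.71 to 1.15 s, with factors of 1.6 and 0.63. With a day-night swing of 150 ms amplitude added, the printed factor is 1.1 or 2.4, depending on when the beat is missed. Further runs gave 1.9 to 3.1. The overall span is 1.1- to 3.1-fold. The SD of RR changes by 0.2% or less in the runs without the swing.

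**Step 5: one missed beat, 288 five-minute values averaged over the day.** The affected window changes 3.9-fold (SD 40 ms) or 2.2-fold (SD 80 ms) as printed. Spread over the day, that is about (3.9 - 1)/288 = 1.0% or (2.2 - 1)/288 = 0.4%. The simulated days moved by 1.2% and 0.5%.

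**Step 6: repeated missed beats, same averaging, 50-ms bins.** At an assumed rate of 1 in 1,000, the share of windows with at least one miss is 1 - 0.999^375 = 31%. The daily value shifts by about +41% (SD 80 ms) to +91% (SD 40 ms) as printed, and by about -19% to -23% in denominator form. At 1 in 10,000 the shifts are about +4% to +12% and -2% to -3%.

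**The case against.** The missing brackets may be only typographical. An inline fraction is often shorthand for everything after the slash, and the cell refers to outside sources for calculation details. In the text available here, a blank and a reference number follow the formula, so a displayed version may have been lost when the PDF was read. This stands: the inline string does not prove that the code will multiply by the range.

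A reader might infer that one missed beat in a day fixes the value. That requires the index to be computed once over the whole day, which the documents do not say. A daily average fits short-window values at least as well, and step 5 then gives about 1%.

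A reader might also infer that the printed form carries no signal, or that the beats are certainly unedited. The first is nearly true only with fine bins and long windows. On the second, the peak-detection package named in SAP 3.4.3 may reject beats; the documents do not say.

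Finally, a reader might extend the criticism to items such as "Respiration rate (breath per minute) [daily average, minimum and maximum values" and ask for percentiles instead. The documents do not support that. The rate of spurious readings would have to be assumed, and the manufacturer supplies respiration rate and temperature by processing that is not shown. Protocol 9.3 itself specifies minimum and maximum values, so percentiles would depart from the protocol.

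What the objection leaves untouched is that the implementation text is ambiguous on the formula, assigns the index to RR intervals beside an NN definition, and gives neither window nor bin width.

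**Conclusion.** The point holds as a minor specification defect. Read literally, the printed index loses most of its response to variability: about -14% to -1% for a 30% fall in spread, against about +77% to +103% with the range in the denominator. These figures assume normal RR intervals and the bins and windows listed.

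Sensitivity to missed beats is uncontrolled rather than known to be large. One miss matters 1.1- to 3.1-fold in a single 24-hour printed value and about 1% under 5-minute averaging. Averaging alone is not enough if misses are frequent, and moving the range to the denominator does not remove the sensitivity either. The miss rates are assumptions; the documents give none.

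The consequence is confined to one of ten HRV variables among 17 sensor variables, in a study that calls itself exploratory. SDNN, RMSSD, pNN50 and LF/HF do not use this formula.

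**What to change.** In SAP 3.4.3:

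1. Write SI = AMo / (2 × Mo × MxDMn), with the brackets.
2. Compute AMo, Mo and MxDMn on NN intervals, after the same abnormal-beat removal as for SDNN.
3. Compute the index in 5-minute segments, the segment length already used for SDNNI, and average the segment values over the day.
4. State the histogram bin width that defines the mode and its amplitude.

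The cost is a few lines of SAP text and a small code change; no new data are needed. The daily minimum and maximum in SAP 2.1.4 can stay as they are.
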